7.3 Adverse Event Reporting

- 7.3.1 In the event of an unanticipated problem or life-threatening complications treating investigators must immediately notify the Overall PI.
- 7.3.2 Investigators **must** report to the Overall PI any adverse event (AE) that occurs after the initial dose of study treatment, during treatment, or within 30 days of the last dose of treatment on the local institutional SAE form.
- 7.3.3 DF/HCC Adverse Event Reporting Guidelines

Investigative sites within DF/HCC will report AEs directly to the DFCI Office for Human Research Studies (OHRS) per the DFCI IRB reporting policy.

7.3.4 Reporting to the Food and Drug Administration (FDA)

The Overall PI, as study sponsor, will be responsible for all communications with the FDA. The Overall PI will report to the FDA, regardless of the site of occurrence, any serious adverse event that meets the FDA's criteria for expedited reporting following the reporting requirements and timelines set by the FDA.

7.3.5 Reporting to Hospital Risk Management

Participating investigators will report to their local Risk Management office any participant safety reports, sentinel events or unanticipated problems that require reporting per institutional policy.

7.4 Routine Adverse Event Reporting

All Adverse Events **must** be reported in routine study data submissions to the Overall PI on the

toxicity case report forms. **AEs reported through expedited processes (e.g., reported to the IRB, FDA, etc.) must also be reported in routine study data submissions.**

7.5 Expedited Reporting to BMS

All SAEs that occur following the subject's written consent to participate in the study through 100 days of discontinuation of dosing must be reported to BMS Worldwide Safety, whether related or not related to study drug. If applicable, SAEs must be collected that relate to any later protocol-specified procedure (eg, a follow-up skin biopsy). Although pregnancy, overdose, potential drug-induced liver injury (DILI), and cancer are not always serious by regulatory definition, these events must be handled as SAEs.

Any component of a study endpoint that is considered related to study therapy should be reported as an SAE (eg, death is an endpoint, if death occurred due to anaphylaxis, anaphylaxis must be reported).

All SAEs must be reported to BMS within 24 business hours of the awareness of the event. SAEs must be recorded on a Medwatch Form 3500A.

SAE Email Address: [contact]

SAE [contact]

If only limited information is initially available, a follow-up report is required and should include the same investigator term(s) initially reported.

If an ongoing SAE changes in its intensity or relationship to study drug or if new information becomes available, a follow-up SAE report should be sent within 24 hours of awareness to BMS (or designee) using the same procedure used for transmitting the initial SAE report.

All SAEs should be followed to resolution or stabilization.

7.6 Expedited Reporting to Exelixis

As soon as an investigator becomes aware of an AE that meets the definition of 'serious,' this must be documented on an SAE Report Form or in an electronic database and include the following: (i) all SAEs that occur after starting cabozantinib and through 30 days after the decision to discontinue study treatment and (ii) any SAEs assessed as related to study treatment or study procedures, from the time of informed consent, even if the SAE occurs more than 30 days after the decision to discontinue study treatment.

All SAEs that are assessed by the PI as **related** to drug or study procedure and all pregnancy/lactation reports regardless of outcome must be sent to Exelixis within one (1) business day of the PI's knowledge of the event. The reports, on a MedWatch 3500A Form, must be sent to [contact] or [contact].

- The PI will perform adequate due diligence with regard to obtaining follow-up information on incomplete reports. All follow-up information must be sent to Exelixis

within one (1) business day of the PI's receipt of the new information. Upon Exelixis request, the PI will query for follow-up information.

[figure not shown]
8 PHARMACEUTICAL INFORMATION

A list of the adverse events and potential risks associated with the investigational agents administered in this study can be found in Section 7.1.

8.1 Cabozantinib

8.1.1 Description

Cabozantinib is the (*S*)-malate salt of cabozantinib, a kinase inhibitor. Cabozantinib (*S*)-malate is described chemically as *N*-(4-(6,7-dimethoxyquinolin-4-yloxy)phenyl)-*N'*-(4-fluorophenyl)cyclopropane-1,1-dicarboxamide, (*2S*)-hydroxybutanedioate. The molecular formula is C₂₈H₂₄FN₃O₅·C₄H₆O₅ and the molecular weight is 635.6 Daltons as malate salt. The chemical structure of cabozantinib (*S*)-malate salt is:

In vitro biochemical and/or cellular assays have shown that cabozantinib inhibits the tyrosine kinase activity of MET, VEGFR-1, -2 and -3, AXL, RET, ROS1, TYRO3, MER, KIT, TRKB, FLT-3, and TIE-2. These receptor tyrosine kinases are involved in both normal cellular function and pathologic processes such as oncogenesis, metastasis, tumor angiogenesis, drug resistance, and maintenance of the tumor microenvironment.

8.1.2 Form

Cabozantinib/XL184 Tablets

The manufacturer will provide each investigator with adequate supplies of cabozantinib, which will be supplied as 20-mg yellow film-coated tablets. The 20-mg tablets are round. The components of the tablets are listed in the table below. The sponsor is requiring pharmacy to dispense cabozantinib in original containers; if needed, it is permissible for DF/HCC pharmacy to remove and destroy the tablets in excess of the dosing requirement per standard practice, while still dispensing the drug in the original container.

Table: Cabozantinib Tablet Components and Composition

Ingredient	Function	%w/w
Cabozantinib Drug Substance (25% drug load as free base)	Active Ingredient	31.7
Microcrystalline Cellulose (Avicel PH-102)	Filler	38.9
Lactose Anhydrous (60M)	Filler	19.4
Hydroxypropyl Cellulose (EXF)	Binder	3.0
Croscarmellose Sodium (Ac-Di-Sol)	Disenegrant	6.0
Colloidal Silicon Dioxide	Glidant	0.3
Magnesium Stearate	Lubricant	0.75
Opadry Yellow Film Coating which includes: - HPMC 2910/Hypromellose 6cp - Titanium dioxide - Triacetin - Iron Oxide Yellow	Film Coating	4.00

8.1.3 Storage and Stability

Store cabozantinib at 20°C to 25°C (68°F to 77°F); excursions are permitted from 15°C to 30°C (59°F to 86°F) [see USP Controlled Room Temperature].

8.1.4 Compatibility

Not applicable

8.1.5 Handling

Qualified personnel, familiar with procedures that minimize undue exposure to themselves and the environment, should undertake the preparation, handling, and safe disposal of the chemotherapeutic agent in a self-contained and protective environment.

8.1.6 Availability

Cabozantinib is an investigational agent and will be supplied free-of-charge from Exelixis.

8.1.7 Preparation

Not applicable

8.1.8 Administration

Cabozantinib is administered once daily as an oral tablet. Participants will be provided with a

sufficient supply of study treatment and instructions for taking the study treatment on days without scheduled clinic visits. After fasting (with exception of water) for 2 hours, participants will take study treatment daily each morning with a full glass of water (minimum of 8 oz/ 240 mL) and continue to fast for 1 hour after each dose of study treatment. If doses are withheld, the original schedule of assessments should be maintained when cabozantinib is restarted. The participant should be instructed to not make up the missed doses and to maintain the planned dosing schedule. Participants must be instructed to not make up missed doses that are vomited.

8.1.9 Ordering

Cabozantinib will be provided by Exelixis.

8.1.10 Accountability

The investigator, or a responsible party designated by the investigator, should maintain a careful record of the inventory and disposition of the agent using the NCI Drug Accountability Record Form (DARF) or another comparable drug accountability form. (See the NCI Investigator's Handbook for Procedures for Drug Accountability and Storage.)

The investigator or designee will maintain accurate records of receipt of all study treatment including dates of receipt. In addition, accurate records will be kept regarding the date, lot number, and how much study treatment is dispensed and used by each subject in the study. Reasons for deviation from the expected dispensing regimen must also be recorded. At completion of the study, to satisfy regulatory requirements regarding drug accountability, all unused study treatment will be reconciled and destroyed according to applicable state, federal, and local regulations.

8.1.11 Destruction and Return

At the end of the study, unused supplies of cabozantinib and nivolumab should be destroyed according to institutional policies. Expired supplies of cabozantinib and nivolumab will be destroyed according to DF/HCC institutional SOP. Destruction will be documented in the Drug Accountability Record Form.

8.2 Nivolumab

8.2.1 Description

Nivolumab is also referred to as BMS-936558-01 or BMS-936558. Nivolumab is a soluble protein consisting of 4 polypeptide chains, which include 2 identical heavy chains and 2 identical light chains. The physical and chemical properties of nivolumab are provided in the table below. The geometric mean of terminal T-1/2 was 25.6 days and the typical clearance was 8.8 mL/h, which are consistent with those of full human immunoglobulin antibodies.

Table: Nivolumab Physical and Chemical Properties

BMS Number	BMS-936558-01
Other Names	Nivolumab, BMS-936558, MDX1106, ONO-4538, Anti-PD-1
Molecular Weight	146,221 daltons (143,619.17 daltons, protein portion)
Appearance	Clear to opalescent, colorless to pale yellow liquid, light (few) particulates may be present
Solution pH	5.5 to 6.5

8.2.2 Storage and Stability

Vials of Nivolumab injection must be stored at 2°-8°C (36°-46°F) and protected from light, freezing and shaking. Shelf-life surveillance of the intact vials is ongoing.

The administration of undiluted and diluted solutions of Nivolumab must be completed within 24 hours of preparation. If not used immediately, the infusion solution may be stored up to 24 hours in a refrigerator at 2°-8°C (36°-46°F) and a maximum of 8 hours of the total 24 hours can be at room temperature (20°-25°C, 68°-77°F) and room light. The maximum 8-hour period under room temperature and room light conditions includes the product administration period.

CAUTION: The single-use dosage form contains no antibacterial preservative or bacteriostatic agent. Therefore, it is advised that the product be discarded 8 hours after initial entry.

8.2.3 Compatibility

No incompatibilities between Nivolumab injection and polyvinyl chloride (PVC), non-PVC/non-DEHP (di(2-ethylhexyl)phthalate) IV components, or glass bottles have been observed.

8.2.4 Handling

Qualified personnel, familiar with procedures that minimize undue exposure to themselves and the environment, should undertake the preparation, handling, and safe disposal of the chemotherapeutic agent in a self-contained and protective environment.

8.2.5 Availability

Nivolumab is available as 100 mg vials (10 mg/mL) with a 0.7mL overfill. It is supplied in 10 mL type I flint glass vials, with butyl rubber stoppers and aluminum seals.

8.2.6 Preparation

Nivolumab is available as 100 mg vials (10 mg/mL), which include an overfill. It is supplied in 10 mL type I flint glass vials, with butyl stoppers and aluminum seals. Nivolumab injection can be infused undiluted (10 mg/mL) or diluted with 0.9% Sodium Chloride Injection, USP or 5%

Dextrose, USP to a final concentration ranging from 1 mg/mL to 10 mg/mL. The total volume of infusion must not exceed 160 mL.

8.2.7 Administration

Nivolumab will be delivered in infusion bags with IV infusion lines over 30 minutes (+/- 10 minutes) using a volumetric pump with 0.2 to 1.2 micron pore size, low-protein binding polyethersulfone membrane in-line filter.

8.2.8 Ordering

Nivolumab will be provided by BMS.

8.2.9 Accountability

The investigator, or a responsible party designated by the investigator, should maintain a careful record of the inventory and disposition of the agent using the NCI Drug Accountability Record Form (DARF) or another comparable drug accountability form. (See the NCI Investigator's Handbook for Procedures for Drug Accountability and Storage.)

The investigator or designee will maintain accurate records of receipt of all study treatment including dates of receipt. In addition, accurate records will be kept regarding the date, lot number, and how much study treatment is dispensed and used by each subject in the study. Reasons for deviation from the expected dispensing regimen must also be recorded. At completion of the study, to satisfy regulatory requirements regarding drug accountability, all unused study treatment will be reconciled and destroyed according to applicable state, federal, and local regulations.

8.2.10 Destruction and Return

At the end of the study, unused supplies of nivolumab should be destroyed according to institutional policies. Destruction will be documented in the Drug Accountability Record Form.

9 BIOMARKER, CORRELATIVE, AND SPECIAL STUDIES

9.1 Correlative Science Objectives

- To explore whether baseline tumor immune cell infiltration and PD-L1 and PD-L2 staining correlates with response to therapy.
- To explore whether changes in circulating immune cell profile correlates with response to therapy
- To explore whether changes in the level of angiogenic and inflammatory blood biomarkers during therapy correlate with efficacy of therapy

9.2 Hypothesis:

Based on what has been described in breast cancer with single agent exposure to Cabozantinib, we hypothesize the following:

- (1) there will be an increase in CD3+ T-lymphocytes, primarily CD8CD4- cytotoxic T lymphocytes
- (2) a decrease in monocytes
- (3) impairment of neutrophil recruitment

In all patients in the run-in phase (first 18 patients) for whom tumor is safely accessible, a baseline and on-treatment tumor biopsy during cycle 2 is required. Based on concerns for biopsy associated complications, a safety evaluation will be performed after 6 patients have undergone an on-treatment biopsy.

For those undergoing a biopsy the following criteria must be met:

- Biopsy should be done only in patients in whom the tumor is safely accessible.
- Due to the risk of perforation and fistula with cabozantinib,
 - transesophageal and transintestinal biopsies should not be performed
 - biopsies should not be performed in areas of prior fistula formation, surgery or radiation.
- **To minimize risks of bleeding, the on-treatment biopsy should be performed with a 20 gauge (or smaller) needle.**

Serial blood draws for correlative science are required on this trial; blood draws will be obtained the first day of cycles 1 and 2 prior to the infusion of study drugs, at the end-of-treatment visit in patients who go off study for progressive disease, and all efforts will be made to obtain an additional blood draw at the time of progressive disease in patients who went off study for anything other than progressive disease.

Summary of Specimens

Research Sampling	Timepoint	Contents	Destination
Archival Tissue	Anytime on study	1 FFPE block or 10-20 5 micron unstained slides	DFCI Clinical Research ([name])
Fresh Tissue	Baseline	5-7 cores	DFCI Clinical Research ([name]) / DFCI [name] Lab
	End of cycle 2	5-7 cores	DFCI Clinical Research ([name]) / DFCI [name] Lab
Stool Sample	Pre-treatment	1 Stool sample	CIO Immune Assessment Lab of [name]
	At time of on treatment biopsy	1 Stool sample	

Blood	Baseline, cycle 2 day 1, cycle 3 day 1, and at progression	5 – Green Top 10 ml Sodium Heparin tubes (REF 366480) (PBMCs)	CIO Immune Assessment Lab of [name]
-------	--	---	---

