9.4 Fresh Tissue Biopsy

Objectives:

- Characterizing immune markers in metastatic well differentiated carcinoid tumors.
- Compare MET and phospho-MET expression in tumor tissue at baseline and after tumor exposure to the combination of MET and PD-1 inhibition.

Collection and Storage of Fresh Tissue

Tissue biopsy samples will be processed with 4-6 cores put in FFPE as per usual institutional practice and a separate core to be put in FFPE to be sent to BWH Pathology.

Details on processing and shipping of samples are provided in Appendix C.

Potential Testing:

Assay 1: Immune population characterization by Multiplex Immunofluorescence (mIF)

Objective: identify subsets of different immune populations (effector/memory CD8 cells, T regulatory cells, dendritic cells, tumor associated macrophages, and Tie-2 expressing monocytes) and changes in these populations in response to cabozantinib and nivolumab at baseline versus 4-6 weeks post initiation of treatment.

Methods: The CIO Tissue Biomarker Laboratory (TBL) led by [name] and [name] offers multiplex immunofluorescence biomarker imaging for multi-label analysis of formalin- FFPE tissue biopsy samples. We use the PerkinElmer's multiplex biomarker imaging systems to precisely measure and quantify multiple fluorescent molecular markers simultaneously, even when co-localized within a single tissue section. The data for each marker is spectrally unmixed, generating clear and accurate images for each of the individual labels in a multi-labeled tissue section with no crosstalk. Specifically, we will use the Opal chemistry and multispectral microscopy Vectra™ 3.0 and Polaris™ systems (Perkin-Elmer), which includes the Nuance software; analysis will be performed using the inForm software. T-cell and other immune cell subpopulations are defined by co-expression of specific markers and are evaluated as cell density per tumor tissue (number of positive cells by mm square of tumor area. The staining procedure is

performed by specialized technicians under pathologist supervision, and the scanning and analysis is done by senior scientists and a pathologist trained in the use of Vectra and InForm.

The following antibodies will be assessed by mIF to identify the presence of the immune subsets:

T Cell Panel: CD4, CD8, FoxP3

Tumor Characteristics Panel: Chromogranin, PD-L1, PD-L2, TIM-3, and LAG-3

Monocyte Panel: CD68, CD 163, Indoleamine 2,3 deosygenase -1 (IDO-1),
CD11c, CD14, CD16, CD56

Assay 2: CyTOF

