	
differential count. Results must be available prior to the administration of study drug. ANC must be ≥ 1500 for eligibility and Cycle 1 Day 1. Subsequent ANC must be ≥ 1000.
 
g. TSH and free T4 will be performed during screening, on Day 1 of Cycles 1-4 and then every other cycle on Day 1.
 
h. Tumor assessments should consist of 1) CT chest/abdomen/pelvis and/or MRI of the abdomen/pelvis, and 2) any other imaging studies (CT neck, plain films, etc.) as clinically indicated by the treating physician. The same radiographic procedures and technique must be used throughout the study for each patient (e.g., if the patient had CT chest/abdomen/pelvis performed during screening, then she should subsequently undergo CT performed using the same radiologic protocol throughout the remainder of the study). Tumor assessments will be performed every 8 weeks (+/- 1 week) calculated from C1D1 for the first 24 weeks, then every 12 weeks (+/- 1 week) thereafter. Additional scans are permitted as clinically indicated. All known sites of disease documented at screening should be re-assessed at each subsequent tumor evaluation. Tumor assessments will occur as outlined regardless of dose holds or treatment delays.
 
i. End of treatment visit is to occur within 30 days of final administration of study treatment. End of treatment assessments do not have to be repeated if the same assessments were performed within 7 days (28 days for tumor assessments) prior to the visit.
 
j. For the first 18 patients during the run-in phase: The first biopsy of a metastatic site should occur during the 2 weeks before initiating treatment on cycle #1. Please see section 9.2. Preferably, the same metastatic lesion will be biopsied twice.
 
k. Five 10mL whole blood sample for research will be collected at baseline, C2D1, C3D1, and progression. The sample will be collected at the end of treatment visit for all patients who discontinue due to progressive disease, and all efforts will be made to obtain an additional blood draw at the time of progressive disease in patients who went off study for anything other than progressive disease.
 
l. If new medications or changes are prescribed while patient is receiving treatment on study, these medications should be recorded.
 
m. Stool sample will be collected during screening, prior to C1D1. Sample should be received within 1 day of collection.
 
n. Stool sample will be collected between the time of the on treatment biopsy and the next planned treatment visit. Sample should be received within 1 day of collection.

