APPENDIX C BIOSPECIMEN PREPARATION

Processing Guidelines for Tissue Biopsies

1. Five to seven cores will be collected utilizing a 16-18 gauge needle is recommended, a 20 gauge core needle biopsy is also acceptable at the discretion of the interventionalist performing the procedure. Collection of less than the goal amount of tissue will not be considered a protocol violation and should be based upon the clinical judgement of the clinician performing the biopsy procedure.
2. Tissue mass is placed on a sterile saline soaked Telpa pad
3. Using forceps or scalpel, tumor tissue is separated into multiple fragments, if necessary
4. Distinct tissue fragments will be allocated for the following, in order of protocol priority:
 - a. Two to three samples placed in room temperature formalin for processing to a FFPE block to be set to the DFCI [name] Lab.
 - b. One sample placed in room temperature formalin to be set to BWH Pathology per BWH CSIR SOP.
 - c. Two to three samples placed in room temperature formalin for processing to additional FFPE block(s) to be stored by the DFCI Clinical Trials Team ([name]).
5. Samples will be annotated with only a unique de-identified study subject number, protocol number, and the date of collection. Links to identifying information for each sample will be stored centrally on a password-protected firewall secured database in accordance with institution tissue bank protocols.

Processing Guidelines for Whole Blood and Plasma Samples

1. Samples will be collected as follows:
 - a. Green Top 10 ml Sodium Heparin Tubes for PBMCs
2. Samples will be delivered immediately to the CIO Immune Assessment Lab to be processed within 1.5 hours of being drawn.

CIO Immune Assessment Lab of [name]:

Center for Immuno-Oncology
Dana-Farber Cancer Institute
[name]
[name]
[contact]
[name]

Processing Guidelines for Stool Samples

1. Samples will be collected per kit instructions.
2. Samples will be delivered immediately to the CIO Immune Assessment Lab to be processed.

CIO Immune Assessment Lab of [name]:

Center for Immuno-Oncology
Dana-Farber Cancer Institute
[name]
[name]
[contact]
[name]

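### Appendix C recommends a wider needle (16-18 gauge) than Section 9.2 allows for the on-treatment biopsy (20 gauge or smaller)

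*Combined protocol and SAP*

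**What the plan says.** Section 9.2 requires a baseline biopsy and an on-treatment biopsy during cycle 2 in the first 18 patients, where tumor can be reached safely. It introduces a list of conditions with "For those undergoing a biopsy the following criteria must be met". The last condition, in bold, opens with its reason, "To minimize risks of bleeding", and then says that "the on-treatment biopsy should be performed with a 20 gauge (or smaller) needle". It gives no gauge for the baseline biopsy. The same section plans that "a safety evaluation will be performed after 6 patients have undergone an on-treatment biopsy". Its specimen table lists 5-7 cores at baseline and 5-7 cores at the end of cycle 2.

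Appendix C, item 1 of the tissue biopsy guidelines, says: "Five to seven cores will be collected utilizing a 16-18 gauge needle is recommended, a 20 gauge core needle biopsy is also acceptable". The 20 gauge option is "also acceptable at the discretion of the interventionalist performing the procedure". The item does not mention baseline or on-treatment.

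Two other places bear on which text a reader would reach. Section 9.4 says "Details on processing and shipping of samples are provided in Appendix C". Study calendar footnote j (Section 10) says "Please see section 9.2. Preferably, the same metastatic lesion will be biopsied twice" and gives no gauge.

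**The concern.** For the on-treatment biopsy, the protocol prefers one needle size in an appendix and calls for a thinner one in the body. The person choosing the needle is an interventionalist, who may be handed the specimen appendix rather than Section 9.2.

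The needle limit is the only condition in the Section 9.2 list aimed specifically at bleeding; the route and site restrictions are there because of perforation and fistula. Other parts of the protocol show why it matters:

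- Section 7.1.1 lists hemorrhagic events as expected with cabozantinib, and Section 6.14 stops the drug for grade 3 or 4 hemorrhage.
- Sections 3.2.11 and 5.4.1 allow low-dose aspirin and stable therapeutic LMWH.
- The calendar schedules the coagulation panel at screening only, and Section 5.2.2 sets no platelet threshold for later cycles.
- The documents give no instruction to hold cabozantinib around the biopsy.

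Two practical consequences follow. The safety evaluation after 6 on-treatment biopsies would be harder to interpret if needle sizes were mixed. And Appendix D, Section 3.7.1 requires all departures from defined procedures to be reported. Appendix C excuses a low core count as not being a violation, but gives no such relief for gauge.

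**Working it through.** This is a comparison of two instructions. The plan gives no figure to reproduce.

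**Direction of the limit.** A higher gauge number means a thinner needle. In Section 9.2, smaller must mean thinner, because only that reading fits the bleeding rationale. The on-treatment limit is therefore 20 gauge or a higher number.

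**The two texts by time point.**

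| Biopsy | Section 9.2 | Appendix C item 1 | Compatible? |
|---|---|---|---|
| Baseline | No gauge set | 16-18 recommended, 20 acceptable | Yes |
| On-treatment (cycle 2) | 20 gauge or thinner | 16-18 recommended, 20 acceptable | Only if the 20 gauge option is chosen |

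**Does Appendix C apply to the on-treatment biopsy?** It names no time point. Its five to seven cores match the 5-7 cores in the specimen table at both baseline and end of cycle 2. Nothing in Section 9.4, the calendar footnotes or Appendix C confines 16-18 gauge to baseline or says which text prevails. It therefore reads as covering both biopsies.

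**Ceiling on exposure.** Inputs: 18 run-in patients (Section 9.2), 6 patients before the biopsy safety evaluation (Section 9.2), and 5 to 7 cores per biopsy (specimen table; Appendix C). On-treatment cores = patients × cores per biopsy.

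- All run-in patients: 18 × 5 = 90 to 18 × 7 = 126 cores.
- Before the safety evaluation: 6 × 5 = 30 to 6 × 7 = 42 cores.

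These counts assume that every run-in patient has accessible tumor and reaches the cycle 2 biopsy, that the full number of cores is taken, and that every operator uses the wider needle. Any departure from these assumptions lowers them.

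**The case against.** The best reply is that the two texts can be followed together. Appendix C is permissive, Section 9.2 is specific to the on-treatment biopsy and states its safety reason, and a specific safety instruction ordinarily governs a general recommendation. A 20 gauge needle complies with both. The calendar carries footnote j, which leads to Section 9.2, on both the research biopsy row and the cycle 2 Day 16-28 column. Section 9.4 cites Appendix C only for processing and shipping. The needle condition also says should, so these are not two absolute rules. Other safeguards remain: biopsy only where tumor is safely accessible, barred routes and sites, fewer cores on clinical judgement, and the evaluation after 6 biopsies.

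Much of this stands. The conflict is partial, a careful reader can find the limit, and the core counts measure possible exposure rather than harm. It does not remove the mismatch. The word should sits under a lead-in that says the criteria must be met. Despite the processing heading, item 1 is a collection instruction: it sets core count and needle size and addresses the person performing the procedure. The other safeguards do not control needle size, and someone working from Appendix C alone would not see the limit.

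**Conclusion.** The concern holds. For the on-treatment biopsy, Appendix C's recommended needle falls wholly outside the limit in Section 9.2, and following that recommendation would defeat the protocol's one bleeding-specific biopsy condition. The conflict is confined to this biopsy; the baseline instructions are consistent.

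The number of patients and cores affected cannot exceed the ceilings above. How far a 16-18 gauge needle would raise bleeding risk in these patients cannot be derived from the documents, so no estimate of harm is offered. The conclusion rests on reading smaller as thinner and on reading Appendix C, which is silent on timing, as covering both biopsies.

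The biopsies serve exploratory objectives. Nothing here affects the objective response rate, the two-stage rule, the sample size or any analysis. It should be corrected as a matter of patient safety and clear instructions.

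**What to change.** Split Appendix C item 1 by time point and leave Section 9.2 unchanged. Suggested wording for the needle instruction:

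> Baseline biopsy: 16-18 gauge recommended; 20 gauge acceptable at the interventionalist's discretion. On-treatment biopsy: 20 gauge or smaller only, meaning 20 or a higher gauge number (see Section 9.2).

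The word only is slightly firmer than the should in Section 9.2, but it fits the lead-in to that list. A bare cross-reference to Section 9.2 for the on-treatment biopsy would also remove the conflict; stating the gauge is safer for an operator who sees only the appendix. The cost is one line in Appendix C, with no change to design, sample size or analysis.
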